Randomization – At each study site the participating physician teams and nursing units will be randomly assigned into one of two study arms (intervention/control). For physician teams, this will occur on a rolling basis for 12 months with 2 physician teams randomly selected at each site each month for participation (1 intervention, 1 control). Once randomized, an email will be sent to the initial attending of the team introducing the study and asking them to reply to the email if they would prefer to opt out and not have their team participate in the randomized controlled trial. If the attending physician from a team refuses to allow their team to participate, the next team identified from the randomized list will be approached to participate. If a new attending joins the team mid-month, they will be approached to participate in the study, but will be automatically assigned to the same randomization group as the rest of their team.

Similarly, a total of 2 medical/surgical units from VAAHS (1 intervention, 1 control) and 4 medical/surgical units from MEDVAMC (2 intervention, 2 control) will be randomly selected to participate in the nurse portion of the project. The nurse manager for each

selected unit will then be approached to obtain approval for the unit to participate. If a nurse manager declines, the next unit on the list will be selected.

For both physicians and nurses, an independent statistician will allocate the teams and units in a concealed fashion, using a computer-generated randomization schema. The physicians and nurses from the intervention groups will receive both independent and group-facilitated mindfulness education, will be encouraged to use a mindfulness mobile app as a practice reminder and additional resource, and instructed to integrate moments of mindfulness with repeated episodes of hand hygiene during the course of caring for patients. The control groups will receive no such education or intervention and will continue as usual.

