The self-directed component will also include a mobile app to serve as an additional self-directed mindfulness practice tool and reminder. We will collaborate with researchers at the National Center for Posttraumatic Stress Disorder, Dissemination & Training Division at the VA Palo Alto Health Care System, to modify and incorporate the Mindfulness Coach (Figure 2). This mobile app contains information on the benefits of mindfulness, mindfulness exercises, strategies for overcoming barriers to practicing mindfulness, mindfulness practice reminders, and the ability to track progress. Mindfulness Coach, available for both iOS and Android platforms, is a free, anonymous, evidence-informed app. The app was originally designed to help Veterans with Posttraumatic Stress Disorder and related mental health concerns and has been updated by incorporating feedback from VA providers and Veterans about their app experiences. We will be employing a research version of the app in coordination with our app development team partners. Nurse participants will be offered the standard Mindfulness Coach Explorer app, while physician participants will be offered a slightly modified version of the mobile app – titled “Mindfulness for Clinicians”. Following randomization, study staff will provide information to participants in the intervention arm to introduce the app, guide participants through features, and encourage use of the app as a tool and reminder for practicing mindfulness. Instructions for how to access the mobile application can be found in Appendix R. Additional reminders to practice mindfulness and incorporate mindfulness during hand hygiene moments will be sent to participants during the intervention period through regular, auto-generated email notifications. The research version of the app also includes push notifications regarding new coaching messages. Deidentified and encrypted app-use metrics will be captured via invitation codes, which unlocks the app and transmits which screens are accessed and duration. App data will be used as a measure of intervention engagement.

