that service rotation on weekdays (3-4 weeks). For the physician teams, which rotate each month, this process will be repeated monthly for 1 year with up to 24 patient-care teams from each participating site. Nurses from both the intervention and control medical/surgical units will be observed for hand hygiene for one month. Observers will be blinded to randomization of the physician teams and thus intervention status. Since nurses remain assigned to one unit for a much longer period of time, nursing units will only participate once during the study. This will result in two nursing units from VAAHHS and four nursing units from MEDVAMC participating. At the completion of the observations, the physicians and nurses will again be asked to complete FFMQ, WBI, and select PSHW questions. To assess sustainability of well-being, mindfulness, and hand hygiene perceptions, we will ask participants to repeat FFMQ, WBI, and select PSHW questions at 6-month post-intervention follow-up points. To assess sustainability of hand hygiene among physicians, select hand hygiene observations at 3 to 12 months post-intervention (based on team schedules) will be conducted. To assess hand hygiene sustainability among nurses, unit-based hand hygiene practices will be reassessed at 1-year post-intervention. To examine changes across survey time points, crosswalk files will be utilized. Participant names will not be on the survey. A study team member will assign the survey respondents an identification number to link repeat surveys.

As part of the intervention we will also collect measures of fidelity. This will include information from the Mindfulness Coach/Mindfulness for Clinicians mobile application including usage and responses from any assessments included in the app about the participant's level of mindfulness. We will also collect data on completion of the Ohio State University STREAM Mind Body modules. This data will be completely de-identified. Both programs do not collect any personal identifiers. Instead, participants will be asked to register with a study assigned code. The de-identified user data for each code will be shared back with the study team to assess fidelity.

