Qualitative data will be collected to better understand the perception of the intervention and assess any barriers or facilitators encountered (**Appendix D**). The primary subjects will be nurses and physicians that participated in the intervention. For this evaluation we will conduct individual or group interviews with approximately 6 nurses and 8 physicians at each site, for a total of 12 nurses and 16 physicians. In addition to the interviews, we will also audio record the site lead/mindfulness champion guided discussions with participants. During these guided discussions it is expected that participants will talk about their insights on learning and their own personal experiences practicing mindfulness during the intervention. All guided discussions, along with the interviews, will be recorded using Audacity software, Microsoft Teams, or Zoom for Government. The discussions and interviews will be conducted in person wherever feasible, however when not feasible, we will use Microsoft Teams, Zoom for Government, or phones to conduct these meetings virtually. The audio recordings will be transcribed and de-identified for analysis. Transcripts will be reviewed and data central to the aims of this study will be extracted and analyzed.

Additional data on fidelity to the intervention will be collected. This will include de-identified usage data from the OSU STREAM modules as well as the Mindfulness Coach/Mindfulness for Clinicians app. For both of these, participants in the intervention will login using a specific project code. No personal identifiers will be collected by either program. De-identified data on usage including the number of people who accessed each module and usage of the Mindfulness Coach/Mindfulness for Clinicians app will be shared with study staff at VA CCMR to evaluate fidelity.

All study data will be stored on a VA Ann Arbor CCMR secure server, accessible only by study staff. To protect subject confidentiality, unique study ID numbers will be used for all study surveys and study databases in lieu of names. Only study staff will have access to the cross-link file that could connect subjects to their ID number. Study documents including signed informed consent documents and data collection/observation sheets will be stored in a locked filing cabinet at each study site. We will follow approved VA guidelines, Records Control Schedule RCS 10-1, for the disposition of records following closure of the study.

RISKS

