Details of each intervention component and measures of fidelity are as follows:

- Participants will be asked to complete self-directed, online mindfulness training modules developed by the Ohio State University Mind-Body STREAM program. The mindfulness training will include three modules: (a) Introduction to Mindfulness, (b) Mindfulness in Daily Life, and (c) Mindful Breathing and Sitting. Participants will be given a unique code to use to access these training modules. The modules will not store or collect any personal identifying information. Consultant [name] will share access data with the Ann Arbor project staff by that access code which will be used to measure fidelity to the intervention.
- As part of the self-directed component participants will be encouraged to use the VA Mindfulness Coach or Mindfulness for Clinicians mobile app. Participants can choose to download this app to their personal devices. Co-investigator [name] at the VA Palo Alto Healthcare System will collect de-identified data on app usage and share with the Ann Arbor team to measure fidelity to the intervention. The mobile app does not collect any personal identifiers.
- The group-facilitated component will include discussions focused on how principles of mindfulness can be used to influence a clinician's state of mental presence, allowing for moments of clarity, insight, and reflection, and potentially enhanced provider and patient safety. Discussions will also address questions and feedback on the self-directed components discussed above. For physician participants, group-facilitated discussions lasting approximately 15 minutes will be offered every other week throughout the intervention phase at each site. For nurse participants, group-facilitated discussions lasting up to 30 minutes will be offered every week throughout the intervention phase at each site. In addition to

recording these discussions for use in the qualitative study evaluation, attendance at these discussions will be recorded to assess fidelity.

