5.6 Data Analysis

Quantitative Statistical Analysis (Aims 1 and 2): Differences in hand hygiene adherence and duration between intervention and control groups will be assessed using Fisher's exact test and t-test, as appropriate. Risk differences in adherence to duration of hand hygiene will be calculated for both intervention and control groups. Because the primary outcomes for Aim 1 (i.e., hand hygiene adherence and duration) are expected to occur frequently, we will use generalized linear models to evaluate differences in hand hygiene adherence and duration for the intervention versus control group, with the Poisson distribution (log link) and robust error variance. Models will account for provider type and level, and will incorporate clustering by physician team (and separately for nursing unit). Statistical significance will be calculated for the intervention (intervention vs. control) coefficient.

As a secondary outcome for Aim 1, we will assess changes and differences in hand hygiene perception based on response to select questions from PSHW. For Aim 2, mindfulness will be based on responses to FFMQ and well-being will be based on responses to WBI. FFMQ and WBI scales will be scored according to the published algorithms. Descriptive statistics will be used to summarize participant scores from pre- and post-intervention, as well as 6-month post-intervention follow-up assessments. Within-group paired-samples t-tests will be used to test for improvement in participant scores across the baseline, post-intervention (~14 days for physicians and 1-month for nurses), and 6-month post-intervention follow-up periods, for the intervention and control groups separately. Analyses will use list-wise deletion for missing data. Participants not completing all surveys will still be included in any analysis for which they provide data. For all analyses, p values less than 0.05 will be considered significant and all tests will be two-tailed. Analysis of covariance (ANCOVA) models will then be used to assess relative changes in mindfulness, well-being, and hand hygiene perceptions across groups, the most direct test of discriminant validity. In these models, post-test scores will be predicted by group status controlling for pre-test scores.

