Mindful Hand Hygiene to
Reduce Infections Among
Veterans While Enhancing
Provider Well-Being

NCT05261282

December 5, 2025

Data Analysis Plan

Differences in hand hygiene adherence and duration between intervention and control groups will be assessed using Fisher's exact test and t-test, as appropriate. Differences in adherence to duration of hand hygiene will be calculated for both intervention and control groups. As a secondary outcome for Aim 1, the investigators will assess changes and differences in hand hygiene perception based on responses to select questions from the PSHW. For Aim 2, mindfulness will be based on responses to the FFMQ and well-being will be based on responses to the WBI. Survey scales will be scored according to the published algorithms. Descriptive statistics will be used to summarize participant scores from baseline and post-intervention, as well as 6-month post-intervention (sustainability) follow-up assessments. Within-group paired-samples t-tests will be used to test for improvement in participant scores across the baseline, post-intervention (~14 days for physicians and 1-month for nurses), and 6-month post-intervention (sustainability) follow-up periods, for the intervention and control groups separately. Participants not completing all surveys will still be included in any analysis for which they provide data. Listwise deletion for observations containing less than 85% complete responses for the FFMQ or WBI items will be used. Missing values for observations with at least 85% responses for the FFMQ or WBI items will be imputed using the average value obtained from non-missing values within each respective subscale. Multilevel linear mixed regression models will be used to assess changes in mindfulness and well-being across groups and the effectiveness of the intervention. Mixed models account for correlation between repeat measurements on the same participant and accommodate missing data across time points. Random effects will be modeled to account for clustering of survey responses at the clinician level. All models will be adjusted for fixed effects for clinician role (physician/nurse) and intervention fidelity. For all analyses, p-values less than 0.05 will be considered significant and all tests will be two-tailed.

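### The SAP's Aim 2 mixed models adjust for intervention fidelity, a post-randomisation variable that exists in one arm only, so the arm estimate need not be the randomised comparison

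*SAP*

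**What the plan says.** The SAP (Data Analysis Plan) gives the purpose of the models: "Multilevel linear mixed regression models will be used to assess changes in mindfulness and well-being across groups and the effectiveness of the intervention". It then fixes the covariates: "All models will be adjusted for fixed effects for clinician role (physician/nurse) and intervention fidelity". The only other Aim 2 tests it names are paired t-tests within each arm, which do not compare arms. It does not define the fidelity variable, its value in controls, whether it changes over time, or whether the effect is an arm main effect or an arm-by-time term.

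The protocol shows what fidelity is:

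- Section 5.1, Intervention Assessment: "As part of the intervention we will also collect measures of fidelity". The list there covers module completion, app use and answers to the app's own mindfulness assessments.
- Section 5.1, Self-Directed Components: "App data will be used as a measure of intervention engagement".
- Section 5.1, Data Collection and Management, on the modules and the app: "For both of these, participants in the intervention will login using a specific project code".
- Section 5.5, on the guided discussions: "attendance at these discussions will be recorded to assess fidelity".
- Section 5.1, Randomization: "The control groups will receive no such education or intervention and will continue as usual".

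Protocol section 5.6 plans an ANCOVA for the same outcomes: "In these models, post-test scores will be predicted by group status controlling for pre-test scores". It has no fidelity term, and the SAP does not repeat it.

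**The concern.** A covariate in a model for a randomised effect should be fixed before randomisation, or at least not be a consequence of assignment. Fidelity is a consequence of assignment and has no counterpart in the control arm. Entering it can change what the arm coefficient means, from the effect of being assigned to the programme to the difference between intervention clinicians who did not engage and all controls. If the programme works through engagement, much of its effect moves from the arm coefficient to the fidelity coefficient. If engagement also tracks a clinician's own level of mindfulness or well-being, the arm coefficient is biased even under a true null.

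The protocol gives reason to expect the second problem. It records prior meditation because this may affect performance during the intervention, and it asks for the modules to be done off duty. There is a further hazard: if the app's mindfulness assessments enter the fidelity variable, the FFMQ model adjusts for a later measure of its own construct.

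At stake are the only between-arm models that the SAP names for Aim 2.

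**Working it through.** **1. The plan's own figure.** Protocol section 5.6 states more than 95% power for FFMQ and WBI at effect sizes of 0.3 to 0.75. At 0.3, two-sided 0.05:

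- Cohen's f, N = 334 to 344, 1 to 3 df: 99.8% or more.
- Paired t-test, n = 167: about 97%.
- ANCOVA, 167 per arm, pre-post correlation 0.65: SE = √(2/167 × (1 − 0.65²)) = 0.083, power 95%.
- Plain two-sample comparison, 167/177: 79%.

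The figure can be reached, but no route to it contains a fidelity term.

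**2. What each coding estimates.**

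| Fidelity coding | Arm estimate |
|---|---|
| 0 in controls, uncentred, arm coefficient read directly | Assignment at zero engagement |
| Time-varying (0 at baseline), arm-by-time read | Assignment at zero engagement |
| Missing in controls | Controls drop out; not estimable |
| 1 for all intervention clinicians, 0 for controls | Collinear with arm |
| Centred within the intervention arm | Randomised comparison, unchanged with complete data |
| Time-invariant main effect, arm-by-time read | Randomised comparison, unchanged with complete data |

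**3. Assumptions for size.** From the protocol: 167/177 and effect size 0.3, taken here as d. Assumed, because the documents give none: three waves, full response, within-person correlation r = 0.6, random intercept, no team or unit clustering, fidelity F between 0 and 1 with 0 in controls. Let k = mean²/variance of F in the intervention arm. It is 1.67 for Beta(1,3), 3 for uniform, 5 for Beta(2,2) and 20 for Beta(5,2).

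**4. Single post score.** SE = √((1 + k)/167 + 1/177). Without fidelity, √(1/167 + 1/177) = 0.108, power 79%. With Beta(2,2), √(6/167 + 1/177) = 0.204, power 31%. The others: Beta(1,3) 0.147 (53%), uniform 0.172 (41%), Beta(5,2) 0.362 (13%).

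**5. Three waves, both post waves pooled.** Without fidelity, SE² = (1 − r) × 1.5 × (1/167 + 1/177) = 0.6 × 0.01164 = 0.00698. So SE is 0.084, and power is Φ(0.3/0.0836 − 1.96) = 95%. Both harmless codings give this same estimate and SE.

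With time-varying fidelity and an effect unrelated to it, the extra variance is [r + (1 − r)/2 − r²] × k/167 = 0.44k/167:

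| F | SE | Power, formula | Power, simulation |
|---|---|---|---|
| Beta(1,3) | 0.107 | 80% | 82% |
| Uniform | 0.122 | 69% | 69% |
| Beta(2,2) | 0.142 | 56% | 56% |
| Beta(5,2) | 0.244 | 23% | 20% |

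The simulation fits the random-intercept model by generalised least squares, with 3,000 runs for Beta(2,2) and 1,200 for the others.

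**6. Effect fully proportional to fidelity.** Each clinician's effect is 0.3 × F/mean(F), which is 0 at F = 0. The coefficient therefore targets 0.00, and simulated rejection is 5–6% for all four distributions.

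**7. True null, engagement correlated ρ = +0.3 with the clinician's own level.** With time-varying fidelity, bias = −(1 − r) × ρ × √r × √k = −0.4 × 0.3 × 0.775 × √k = −0.093√k. This gives −0.12, −0.16, −0.21 and −0.42 in the order of the table. For Beta(2,2), 0.208/0.142 = 1.46, so false rejection is about 31% (32% simulated). If the arm coefficient is read directly with the baseline wave pooled in, bias = −ρ√r√k = −0.52 for Beta(2,2), with 85% false rejection. At ρ = −0.3 the signs reverse.

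**8. A second set of assumptions.** Fidelity is 0 to 3 modules (mean 1.6, coefficient of variation 0.7), r = 0.65, and post scores are modelled on arm, baseline score and uncentred fidelity. A true 0.30 is estimated as 0.30, 0.15 or 0.00 when none, half or all of the benefit runs through fidelity. With an added trait correlation of 0.3 these become 0.18, 0.04 and −0.11. Without the fidelity term the estimate is 0.30 throughout with complete data.

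**The case against.** The strongest reply is that this is an unspecified coding, not a demonstrated bias. The SAP speaks of changes across groups and lists fidelity beside clinician role, a fixed characteristic. That wording suits an arm-by-time model with fidelity as a time-invariant main effect, which is harmless with complete data. This stands: bias is not certain. But the SAP does not commit to that coding, and under it the term does nothing for the arm effect. It also protects only the arm-by-time coefficient. In the second set of assumptions, the arm difference at follow-up evaluated at zero fidelity still ranged from 0.30 down to −0.22.

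Other points have force:

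- The −0.52 and 85% need a direct arm coefficient with baseline pooled in, which fits the SAP's wording poorly.
- The bias depends strongly on the assumed fidelity distribution.
- A zero estimate is an extreme. Intervention clinicians also receive emails, a guide, dispensers and contact with champions, which the listed fidelity measures do not capture.
- The protocol's ANCOVA is not expressly withdrawn. Even so, it does not repair the model that the SAP does specify.

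One real use of fidelity remains. With 30% of surveys lost in a way tied to fidelity, the second simulation gave up to 0.35 without the term, about 0.33 with the time-invariant term and 0.30 with within-arm centring (truth 0.30). That supports using fidelity as an auxiliary variable for missing surveys, not an undefined covariate in the effect model.

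**Conclusion.** The concern holds. The SAP's only named between-arm models for FFMQ and WBI condition on a variable that is measured after randomisation and in one arm. That follows from the documents and rests on no assumed number. Under two codings the term leaves the arm estimate unchanged with complete data. Under the others the estimate answers a different question, loses precision, is biased in a direction the documents do not determine, or cannot be computed.

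The sizes are illustrative, since the documents give no fidelity distribution, engagement-trait correlation or within-person correlation. The scope is limited to Aim 2: the SAP's Fisher's exact test and t-test for adherence and duration carry no covariates. This should be settled before the Aim 2 models are run.

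**What to change.** In the SAP, remove intervention fidelity from every Aim 2 model that estimates the arm effect. State the model as arm, time, arm-by-time and clinician role with the clinician random effect, and name arm-by-time as the contrast of interest.

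Move fidelity to a separate analysis labelled exploratory, such as dose-response within the intervention arm or a complier average causal effect. Define the fidelity measure there, and say whether the app's mindfulness assessments count towards it. A complier analysis must state that it assumes no effect of assignment in those who do not engage, which the emails, guide and dispensers make doubtful. If survey loss may depend on fidelity, use fidelity in an imputation model as a sensitivity analysis.

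The cost is one phrase removed and one contrast stated. No new data are needed. With complete data, precision equals that of either harmless coding and is better than under the others.
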